14.1 Overview

This is a single-arm Phase II trial with the primary objective of determining whether MRI-targeted boost SRT (MTSRT) improves the rate of PSA response (i.e., PSA < 0.1 21 months post treatment completion) in men receiving radiation therapy due to rising PSA post-prostatectomy. Secondary objectives include evaluation acute and late occurring toxicity, quality of life, biochemical and clinical failure, and survival. Additionally, blood and biopsy tissue samples from study patients will provide data for various biomarker studies described in the Bankhead Coley Team Science project "Integrated biomarkers for individualized prostate cancer therapy".

A single stage design without interim analysis of the primary endpoint is proposed for this trial because it would not be practical or desirable to suspend accrual to accommodate an interim assessment of PSA response, which requires nine months follow-up. Moreover, PSA response is not a perfect near term surrogate for long term benefit and thus not a definitive basis for an early conclusion regarding efficacy. The trial involves standard therapy with dose escalation, and an evaluation of PSA response based on accrual of 40 evaluable patients will provide information needed to design a subsequent trial evaluating long term outcome. Early stopping rules based on monitoring the toxicity of study treatment are provided in Section 14.6.

14.2 Sample size, accrual rate and study duration

Sample size is based on the primary objective of demonstrating that MTSRT increases the rate of PSA response to treatment, by which we mean undetectable PSA level (<0.1) when assessed 21 months after completing treatment. We expect the PSA response rate in the standard SRT to be 60%. [50] Assuming sufficient follow-up to determine PSA nine months post treatment, a total of 40 patients in the single-arm study provides 83.9% power to detect an absolute increase of 20% in the PSA response rate, from 60% to 80%, using a one-sided Fisher's exact test with 5% significance level. To ensure a minimum of 40 study patients evaluable for PSA response as our main study endpoint, we plan to enroll a total of 44 patients assuming 10% drop-out.

We plan to accrue 1 patient per month during the first year of this protocol. After the ramp-up phase is completed, we anticipate 1.5 patients per month. This rate was also calculated considering increasing prostate cancer volumes due to expansion of the department (anticipated growth at Sylvester main and Deerfield branch). Thus accrual will be complete in about 3 years; 12 in year 1 and 18 per year in year 2 and 3. Patients will be followed for a minimum of five years, giving total study duration of 8 years. The main efficacy endpoint will be analyzed after enrollment is complete and all patients have been

assessed for PSA response nine months post treatment, and a final efficacy analysis of all endpoints will be carried out at the conclusion of study when patients have been followed for 5 years. Analyses of some secondary endpoints, including acute toxicity, psychosocial parameters, and biomarker distribution on US guided biopsies, and initial MRI findings may be reported before the efficacy analyses. These secondary endpoints will be analyzed after all planned patients have been accrued, completed treatment and have a minimal potential follow-up of 3 months from the end of RT.

14.3 Definitions and endpoints:

Evaluable: Patients who are study eligible and receive an initial dose of *MTSRT* will be considered *evaluable for safety*, regardless of whether or not the full course of radiation treatment is completed according to protocol. To be *evaluable for efficacy*, study eligible patients must either (1) complete radiation treatment and the nine month post treatment PSA assessment or (2) initiate therapy but develop evidence of biochemical or clinical failure, or die from causes related to prostate cancer, within nine months of stopping or completing treatment. In the latter case (2), which is expected to be rare, patients will be included as non-responders in the evaluation of PSA response rate. The set of patients who are evaluable for efficacy comprise the main analysis set.

Exclusions: Any patient who is enrolled on study but does not receive an initial dose of radiation treatment will be excluded from all efficacy analyses. Any patient who initiates treatment and is later found to be ineligible for study (e.g., protocol violation) will be withdrawn from study but will be followed for toxicity and clinical outcome; the experience of such patients will be characterized separately from that of patients who are evaluable for efficacy. Reasons for exclusion of enrolled patients from analysis of safety or efficacy will be characterized.

Study endpoints are defined in **Section 9.1**.

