3.0 PATIENT SELECTION

Up to 80 participants will be accrued for the entire study (Phase II and Phase III). The study is currently in Phase II which will accrue up to 40 participants. For a description of the Phase III component of the trial, please refer to protocol version 7.0, dated 10/14/2015.

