14.5 Analysis plan

The main analysis of study findings will be done for all patients who meet evaluable criteria as stated in Section 14.3. As noted above, analyses of some secondary endpoints, including acute toxicity, psychosocial parameters, tissue and blood product-related biomarker distribution on US-guided biopsies, and initial MRI findings may be reported before the efficacy endpoints, including the primary endpoint. These secondary endpoints will be analyzed after all planned patients have been accrued, completed treatment and have a minimal potential follow-up of 3 months from the end of RT. An initial analysis of clinical outcome (efficacy) is planned after all patients have been assessed for PSA levels at 9 months and a final analysis will be done at the completion of the planned 5 year follow-up of all study patients. Statistical tests will be two-sided with 5% significance level.

Statistical analysis will include descriptive statistics for patient demographics and baseline disease characteristics. Counts and percentages will be used to summarize the distribution of categorical variables while median, range, mean and standard deviation will be used for continuous variables. Baseline characteristics will include age, race/ethnicity, PSA, PSA doubling time, pT-category, pathologic Gleason score, and performance status. Biomarker measurements and proteomic/genomic profiles obtained from baseline biopsy will also be summarized with descriptive statistics.[51]

Treatment received will be summarized by the number and duration of treatment delays, and the rates of discontinuation or completion. Safety analysis will include a detailed tabulation of acute and late occurring toxicity by type and grade. Additionally, we will estimate the cumulative incidence (from start of treatment) of grade 2+ and 3+ genitourinary (GU) toxicity and of grade 2+ and 3+ gastrointestinal

(GI) toxicity. Death without the toxicity of interest will be treated as a competing risk, and toxicity rates will be reported.

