The primary trial endpoint, *PSA response rate*, will be estimated as a proportion with corresponding 95% confidence interval by the exact binomial method. Biomarker and proteomic/genomic characteristics of baseline prostate bed biopsy tissue will be summarized by descriptive statistics. Additionally, biomarker and proteomic/genomic characteristics measured in blood samples obtained at baseline, RT completion, and 3 months post RT will also be studied and changes from baseline will be tested for significance using t-test (means) or McNemar's test (proportions) for paired data. (For biomarker studies, nonparametric tests or data transformations to attain approximate normal distributions will be applied as needed.) Logistic regression models will be used to investigate the association between baseline factors, including biomarkers and proteomic/genomic profiles, and PSA response. Changes in biomarkers and proteomic/genomic characteristics measured in blood will also be investigated for association with PSA response.[52]

Patients will be followed for disease progression and vital status for a period of five years after completing study treatment. Progression of disease will be categorized as biochemical failure (BF), clinical failure (CF), or combined (BF + CF), where combined failure refers to documented evidence of BF and CF occurring within 6 months of each other with the earlier date used. CFs will be further categorized as local, nodal, or distant. Start of subsequent therapy will be considered a failure event for selected analyses as indicated in the table below. Deaths will be categorized as related/unrelated to prostate cancer. The number of observed failures will be tabulated by failure type. Similarly, vital status will be tabulated by presence or absence of disease at last follow-up.

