To illustrate the stopping guidelines, suppose that 4 patients have been assessed for toxicity and 3 of them have experienced grade 3 treatment-related toxicity during or within 3 months of completing radiotherapy (second row, left panel). Under this circumstance, the observed rate of acute G3+ toxicity is 37.5%, resulting in a posterior probability of 90.4% that the true underlying rate exceeds 15% thus suggesting early termination of the study due to acute toxicity. Similarly for late G3+, suppose that a total of 8 patients have been followed sufficiently for assessment of late toxicity and 2 have experienced grade 3 treatment-related toxicity starting more than 3 months after treatment completion (first row, right panel). These data give a 25% observed rate of late G3+ toxicity and a posterior probability of 82.6% that the true underlying rate exceeds 10% thus suggesting early termination of the study due to late toxicity.

Posterior probabilities used to derive guidelines for acute toxicity are calculated under a prior beta distribution with parameters $\beta_1 = 0.3$ and $\beta_2 = 1.7$, which corresponds to an expected rate of 15% based

on prior information roughly equivalent to having studied 2 patients. Furthermore, this prior distribution assigns a small a priori chance (32%) to the possibility that the true rate of unacceptable toxicity is 15% or greater. For late toxicity, the parameters of the prior distribution are $\beta_1 = 0.2$ and $\beta_2 = 1.8$, giving an a priori chance of 27% that the true rate of late toxicity is 10% or greater.

No early stopping for efficacy. We do not propose early stopping of this trial based on interim assessment of efficacy for the following reasons. First, it would not be practical or desirable to suspend accrual to accommodate an interim assessment of the primary efficacy endpoint, PSA response, which requires nine months follow-up. Moreover, PSA response is not a perfect near term surrogate for long term benefit and thus not a definitive basis for an early conclusion regarding efficacy. The trial involves standard therapy with dose escalation, and an evaluation of PSA response based on accrual of 24 evaluable patients will provide information needed to design a subsequent trial evaluating long term outcome.

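### The stated 83.9% power belongs to a one-sided 5% test, but the analysis plan makes tests two-sided at 5% without exempting the primary endpoint; on that rule power is 73.2%

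*Combined protocol and SAP*

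**What the plan says.** Section 14.2 assumes a 60% PSA response rate with standard salvage radiotherapy. Of the 40 men in the single arm it says that this number "provides 83.9% power to detect an absolute increase of 20% in the PSA response rate, from 60% to 80%, using a one-sided" test. The level is 5%, and the test it names is Fisher's.

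Section 14.5, the analysis plan, says "Statistical tests will be two-sided with 5% significance level". For the primary endpoint it says only that the response rate "will be estimated as a proportion with corresponding 95% confidence interval by the exact binomial method". It names no test against 60%, no one-sided bound and no number of responders that would count as success.

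The sample-size statements also differ:

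- Section 14.2 wants at least 40 men evaluable for the primary endpoint and sets enrolment above that: "we plan to enroll a total of 44 patients assuming 10% drop-out".
- Section 3.0, repeated in 14.0: "The study is currently in Phase II which will accrue up to 40 participants".
- Section 14.1: "an evaluation of PSA response based on accrual of 40 evaluable patients will provide information needed to design a subsequent trial".
- Section 14.6, in what is otherwise the same sentence: "an evaluation of PSA response based on accrual of 24 evaluable patients will provide information needed to design a subsequent trial".

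**The concern.** The trial is sized on one test, and the analysis section describes another. Section 14.1 sets the primary objective as finding out whether the boost improves the PSA response rate, so a rule is needed for when the result beats 60%. An analyst following 14.2 would use a one-sided 5% test. An analyst following 14.5 would use a two-sided 5% test, or check whether the 95% interval lies above 60%. The second rule is stricter, and the stated power does not apply to it.

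At a borderline result the conclusion would depend on the section followed, and nothing in the plan prevents that choice from being made once the data are known.

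The test name adds to the uncertainty. Fisher's exact test compares two groups, and this design has one group and a fixed reference rate.

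**Working it through.** **Inputs.** All from 14.2 unless noted: reference rate p0 = 0.60, target rate p1 = 0.80, n = 40 evaluable; α = 5% one-sided (14.2) or 5% two-sided (14.5).

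**Method.** X is the number of responders, binomial(n, p). For a cutoff r, the upper-tail error is P(X ≥ r | 0.60) and power is P(X ≥ r | 0.80). The cutoff is the smallest r whose upper-tail error is at most 0.05 (one-sided) or 0.025 (two-sided, equal tails). The latter is the same as requiring the lower limit of the exact (Clopper-Pearson) 95% interval to exceed 60%.

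**Step 1: the plan's own figure, n = 40.**

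| Cutoff r | P(X ≥ r given 0.60) | P(X ≥ r given 0.80) |
|---|---|---|
| 29 | 0.0709 | 0.9125 |
| 30 | 0.0352 | 0.8392 |
| 31 | 0.0156 | 0.7318 |

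One-sided at 5%, 29 fails (0.0709 > 0.05) and 30 passes. Power is 83.9%, which reproduces 14.2. The figure is therefore that of a one-sample exact binomial test. A genuine two-group one-sided Fisher's test would have 29.0% power with 20 per arm, or 53.8% with 40 per arm.

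**Step 2: the rule in 14.5, n = 40.** The upper tail must be at most 0.025, so 30 fails (0.0352) and 31 passes (0.0156). Power is 73.2%. The equal-tail test, the minimum-likelihood two-sided test and the exact 95% interval all give 31.

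**Step 3: where the rules disagree.** Only at 30/40 (75%).

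- One-sided p = 0.035: success.
- Two-sided p = 0.054 (minimum likelihood) or 2 × 0.0352 = 0.070 (doubled): not success.
- Exact 95% interval 58.8% to 87.3%: includes 60%.
- Exact 90% interval 61.3% to 85.8%: excludes 60%, in line with the one-sided test.

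P(X = 30 | 0.80) = 0.1075, which is the whole power gap: 0.8392 − 0.7318 = 0.1074 (the last digit is rounding).

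**Step 4: other evaluable numbers.** Enrolling 44 could leave 40 to 44 evaluable. The two-sided columns use the equal-tail (exact 95% interval) rule.

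| n | One-sided cutoff | Power | Two-sided cutoff | Power | One-sided α if the cutoff stayed at 30 |
|---|---|---|---|---|---|
| 40 | 30 | 83.9% | 31 | 73.2% | 3.5% |
| 41 | 31 | 81.8% | 32 | 70.4% | 5.7% |
| 42 | 31 | 88.2% | 32 | 79.5% | 8.6% |
| 43 | 32 | 86.4% | 33 | 77.1% | 12.4% |
| 44 | 33 | 84.6% | 34 | 74.6% | 17.0% |

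The criterion therefore has to follow the actual evaluable number.

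**Step 5: the cap of 40.** If 14.2's 10% drop-out is applied to 40 enrolled, 40 × 0.9 = 36 are evaluable. The one-sided cutoff is then 27 with power 83.2%; the two-sided cutoff is 28 with power 71.6%. The 36 is a favourable point, because exact power moves in steps: one-sided power is 74.5% at 35, 80.9% at 37 and 78.5% at 38.

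**The case against.** The strongest reply is that 14.2 is specific and 14.5 is general. Section 14.2 names the endpoint, both rates, the sidedness and the level in advance. The sentence in 14.5 sits in a section that goes on to paired tests and regression models. For the primary endpoint 14.5 prescribes estimation only, so the two-sided sentence has no named primary test to act on. Reporting a conventional 95% interval beside a one-sided design test is not in itself contradictory. This is a fair reading, and under it 83.9% stands. But the plan does not say so, and the only interval it specifies agrees with the two-sided rule. If the interval is pure estimation, 14.5 contains no primary test and the power statement describes an analysis that is not planned.

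A second point is that two-sided exact tests do not all agree away from n = 40. At 33/44 the minimum-likelihood p-value is 0.0455, so that test needs 33 and has 84.6% power, the same as the one-sided rule. This is correct. The two-sided figures in Step 4 hold for the exact 95% interval that 14.5 names, not for every two-sided test. The 73.2% at n = 40 does not depend on the choice.

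Third, this is a single-arm Phase II trial meant to inform a later one, and only one outcome is in dispute. That limits the harm but does not settle the rule.

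**Conclusion.** The inconsistency is real. The 83.9% is correct for a one-sided 5% exact binomial test in 40 evaluable men. Under the two-sided 5% rule in 14.5, power is 73.2%, which is 10.7 percentage points lower, and the requirement rises from 30 to 31 responders. This rests on the plan's own 60% and 80% rates and on 40 evaluable men. It is an unresolved choice between two rules rather than a proven loss of power: if 14.2 governs, nothing is lost, but 14.5 must say so. It should be fixed before the primary analysis.

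Three related slips are minor and do not drive this conclusion: the Fisher label for a one-sample comparison, the cap of 40 participants against 44 to be enrolled, and the 24 in 14.6, evidently a leftover.

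**What to change.** 1. In 14.2, replace Fisher's exact test with the one-sample exact binomial test against 60%.
2. Choose one rule before analysis and state it in both 14.2 and 14.5:
   - **(a)** Keep one-sided 5%, exempt the primary endpoint from the two-sided sentence in 14.5, and report a one-sided 95% lower bound (equivalently a two-sided 90% interval). Power stays at 83.9%.
   - **(b)** Keep two-sided 5% with the exact 95% interval and restate power as 73.2% at n = 40.
3. Define success for the actual evaluable number: the exact lower bound exceeds 60%. For n = 40, 41, 42, 43 and 44 the cutoffs are 30, 31, 31, 32 and 33 under (a), and 31, 32, 32, 33 and 34 under (b).
4. Make 3.0, 14.0, 14.1, 14.2 and 14.6 agree on one enrolled and one evaluable number, and correct the 24 in 14.6.

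**Cost.** Option (a), the test name and the 24 need wording only. Option (b) lowers the stated power. Regaining at least 83.9% with the exact 95% interval is first possible at 48 evaluable men (36 responders, upper-tail error 2.2%, power 85.2%). Raising the cap to match 14.2 adds 4 men. Keeping it at 40 adds none, but leaves about 36 evaluable at the assumed drop-out, with the power shown in Step 5.

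### Section 14.2 enrols 44 to secure at least 40 evaluable, but 10% drop-out leaves 39.6 expected; Section 14.6 says 24 evaluable where 14.1 and 14.2 say 40. Both need correcting; power is almost unaffected.

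*Combined protocol and SAP*

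**What the plan says.** Section 14.2 bases the design on 40 evaluable patients: "a total of 40 patients in the single-arm study provides 83.9% power to detect an absolute increase of 20% in the PSA response rate". The two rates compared are 60% and 80%, and the level is 5%, one-sided. The section then sets 40 evaluable as a minimum to be secured and gives the enrolment meant to secure it: "we plan to enroll a total of 44 patients assuming 10% drop-out".

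Section 14.1 agrees with the 40. It justifies the single-stage design by an evaluation of PSA response "based on accrual of 40 evaluable patients". Section 14.6 gives the same justification in nearly the same words, as a reason for not stopping early for efficacy, but refers to "an evaluation of PSA response based on accrual of 24 evaluable patients".

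Section 14.3 defines who is evaluable for efficacy. These are eligible patients who complete radiotherapy and the nine-month PSA, plus those who start treatment and fail, or die of prostate cancer, within nine months. The second group counts as non-responders.

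**The concern.** The enrolment figure is offered as securing a minimum, yet it equals the target multiplied by 1.10 rather than divided by 0.90. A plan that loses 10% of those enrolled has to divide by the fraction retained. Taken at its word, Section 14.2 promises a number of evaluable patients that its own drop-out rate does not deliver.

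The two evaluable numbers, 40 and 24, both stand in current text. A monitoring committee member who reads Section 14.6 alone would be misinformed about the size of the efficacy analysis.

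What could be at stake is the stated 83.9% power. That has to be checked rather than assumed, because exact tests do not lose power smoothly as the sample shrinks.

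**Working it through.** **Inputs.** Null rate 60%, alternative 80%, one-sided 5% level, 40 evaluable, 83.9% power, 44 enrolled and 10% drop-out are all from Section 14.2. The 40 in Section 14.1 and the 24 in Section 14.6 are as quoted above. Drop-out is read as the share of enrolled patients who do not become evaluable for efficacy.

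**1. Reproduce the stated power.** With n evaluable, take the smallest r for which P(X ≥ r | n, 0.60) ≤ 0.05. Power is then P(X ≥ r | n, 0.80). For n = 40, r = 30, the exact level is 0.0352 and the power is 0.8392. This matches the stated 83.9%. Section 14.2 calls the test Fisher's exact, but the figure is that of the one-sample exact binomial test.

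**2. Check the inflation.**

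- Expected evaluable with 44 enrolled: 44 x (1 − 0.10) = 39.6.
- Enrolment needed for an expected 40: 40/(1 − 0.10) = 44.4, so 45 (45 x 0.90 = 40.5).
- Source of the 44: 40 x 1.10 = 44.
- Loss rate at which 44 gives exactly 40: 4/44 = 9.1%.

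**3. Power by number actually evaluable** (one-sided 5%, 60% against 80%):

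| Evaluable | Responders needed | Exact power |
|---|---|---|
| 36 | 27 | 83.2% |
| 37 | 28 | 80.9% |
| 38 | 29 | 78.4% |
| 39 | 29 | 85.9% |
| 40 | 30 | 83.9% |
| 41 | 31 | 81.8% |
| 42 | 31 | 88.2% |
| 43 | 32 | 86.4% |
| 44 | 33 | 84.6% |

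Power moves up and down because the cut-off is a whole number. One patient below target, at 39, it is higher than at 40; one above, at 41, it is lower.

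**4. Average over random loss.** Suppose each enrolled patient is independently evaluable with probability 0.90. The documents give no such model, so this is an assumption. Average power with N enrolled is the sum over k of C(N,k) x 0.9^k x 0.1^(N−k) x power(k).

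| Enrolled | Chance of at least 40 evaluable | Average power |
|---|---|---|
| 44 | 54.7% | 83.3% |
| 45 | 70.8% | 84.1% |

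The slip therefore costs about 84.1 − 83.3 = 0.8 percentage points of average power.

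**5. The 24.** The toxicity stopping table in Section 14.6 runs to 40 patients for both acute and late toxicity. The power in Section 14.2 is stated for 40. No calculation in Section 14 uses 24.

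**The case against.** The strongest reply is that one patient is planning rounding. A loss of 9.1% instead of a round 10% gives exactly 40. Section 14.3 keeps some early failures as evaluable non-responders, so not every early stop is a loss. The accrual forecast in Section 14.2 (12 + 18 + 18 = 48 over three years) leaves room for a 45th patient. All of this stands, and it is why the point is minor. It does not rescue the wording, because the text claims to secure a minimum and states the 10% itself.

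A reader might infer that the trial is underpowered because the minimum is missed. The figures do not support that. Power at 39 evaluable exceeds the stated value, the average is 83.3%, and the remaining variation comes from the discreteness of the exact test under any inflation formula. Nor should the 45.3% chance of falling short of 40 (100 − 54.7) be blamed on the slip. With 45 enrolled the chance is still 29.2% (100 − 70.8), since inflating to an expected value never guarantees a minimum.

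A reader might also infer from Section 14.6 that an analysis of 24 patients is planned. No section plans one. The number appears only in a narrative reason for not stopping early, and is best treated as unreconciled text.

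**Conclusion.** Wrong as written, and minor. The enrolment of 44 does not deliver the stated minimum of 40 at the stated 10% drop-out: the expectation is 39.6, one patient short of the correct inflation. Section 14.6 contradicts Sections 14.1 and 14.2 on the evaluable number. The effect on power is negligible: 83.3% on average with 44 enrolled, against 83.9% stated for exactly 40.

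This rests on the one-sided test that reproduces the plan's figure and, for the averages, on independent 10% losses. It also takes 44 as the enrolment. Sections 3.0 and 14.0 limit Phase II to 40 participants, and Section 14.5 makes tests two-sided; those are separate matters that this point does not settle.

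**What to change.** In Section 14.2, replace the claim of a secured minimum with a statement along these lines:

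> Enrolling 44 is expected to give about 40 evaluable patients (39.6 at 10% loss; exactly 40 at about 9% loss). The number of responders needed and the exact power depend on the number actually evaluable; over 36 to 44 evaluable, power ranges from 78.4% (at 38) to 88.2% (at 42).

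In Section 14.6, change 24 evaluable to 40, to match Sections 14.1 and 14.2.

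The cost is a few words in two sections. No patients are added, and neither the test nor the 83.9% at 40 evaluable changes. Enrolling 45 would also correct the arithmetic, but would still not guarantee 40 evaluable, so the wording should change in either case.

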4.11 Duration of Therapy

- The therapy will be delivered over approximately 7– 8 weeks.
- Treatment will be stopped for grade 4 acute toxicity (according to the current version of Common Terminology Criteria for Adverse Events (CTCAE version 4), but may be resumed per protocol if the treatment break is less than 10 working days. Since we have never observed grade 4 toxicity acutely using IMRT such an event is unlikely. If grade 4 toxicity resolves beyond the 10 days the treating physician will decide whether to give additional RT.
- Treatment will be stopped if metastasis is detected by radiographic or pathologic evidence and the patient will be removed from the study, but not from intent-to-treat analysis. A work-up for metastasis during treatment will only be carried out if the treating physician deems necessary.
- In case that the 2-year MRI exam identifies a suspicious for cancer lesion, US-guided biopsies will be taken.

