12.0 CRITERIA FOR DISCONTINUATION OF THERAPY

Treatment will be stopped for grade 4 acute toxicity (according to the current version of Common Terminology Criteria for Adverse Events (CTCAE version 4), but may be resumed per protocol if the treatment break is less than 10 working days. If grade 4 toxicity resolves beyond the 10 days the treating physician will decide whether to give additional RT.

Treatment will be stopped if metastasis is detected by radiographic or pathologic evidence and the patient will be removed from the study. A work-up for metastasis during treatment will only be carried out if the treating physician deems necessary.

Patients may discontinue therapy at the treating physician's discretion, i.e. due to non-compliance. Patients may withdraw their consent at any time.

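### The main efficacy set selects treated men on what happens after treatment starts, and no all-treated analysis of PSA response stands beside it

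*Combined protocol and SAP*

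**What the plan says.** **Main set.** Section 14.3 gives two ways to be evaluable for efficacy. Under the first, an eligible man must "complete radiation treatment and the nine month post treatment PSA assessment". Under the second, he must "initiate therapy but develop evidence of biochemical or clinical failure, or die from causes related to prostate cancer, within nine months of stopping or completing" radiotherapy. Of men in this second group the section says that "patients will be included as non-responders in the evaluation of PSA response rate". The section then states: "The set of patients who are evaluable for efficacy comprise the main analysis set". Section 14.5 applies it: "The main analysis of study findings will be done for all patients who meet evaluable criteria as stated in Section 14.3". For men left out, 14.3 asks only that the reasons be described.

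**Endpoint.** Section 9.1 defines PSA response over study patients, as PSA below 0.1 ng/mL at 21 months. It sets biochemical failure at nadir + 2 ng/mL and lists local criteria only for clinical failure. Section 14.5 divides clinical failures into local, nodal and distant.

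**Metastasis during treatment.** Section 4.11 says that "the patient will be removed from the study, but not from intent-to-treat analysis". Section 12 repeats the rule without the last clause: "Treatment will be stopped if metastasis is detected by radiographic or pathologic evidence and the patient will be removed from the study". Section 14 defines no intent-to-treat or all-treated set.

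**The concern.** Membership of the main set is decided after treatment begins. Three groups of treated men can meet neither route: those who stop radiotherapy early without a qualifying failure (Section 12 allows stopping for grade 4 toxicity, non-compliance or withdrawal), those with no nine-month PSA, and those who die of another cause first.

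The second route does not catch every non-responder, because response and failure use very different cut-offs. A man who stops radiotherapy early with a PSA above 0.1 but below nadir + 2 ng/mL is not a responder, yet he is dropped rather than counted against the treatment.

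If the men dropped respond less often than the men kept, the observed rate is too high. In a randomised comparison part of this might cancel between arms. Here the rate is set against a fixed 60%, so nothing offsets it.

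**Working it through.** **Inputs.** Null rate 60%, alternative 80%, 40 evaluable men, one-sided 5%, stated power 83.9%, and 44 enrolled to allow for 10% drop-out (Section 14.2). Two-sided 5% testing and an exact 95% confidence interval (Section 14.5). The documents give no response rate *q* for excluded treated men, so *q* is an assumption and is varied. That all 44 men are treated and that 4 of them are excluded are also assumptions, taken from the 14.2 planning figures.

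**1. The plan's own figure.** With X ~ Binomial(40, p), the smallest count with P(X ≥ r | 0.60) ≤ 0.05 is r = 30:
- P(X ≥ 29 | 0.60) = 0.071 and P(X ≥ 30 | 0.60) = 0.035.
- P(X ≥ 30 | 0.80) = 0.839, which reproduces 83.9%. The figure is that of a one-sample exact binomial test, although 14.2 calls it Fisher's exact test.
- Two-sided 5% needs 31/40: upper tail 0.016, power 73.2%. This matches the exact 95% interval, whose lower limit is 58.8% at 30/40 and 61.5% at 31/40.

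**2. Effect of the exclusions.** Hold the true all-treated rate at 60% and exclude 4 of 44 men who respond at rate *q*. The rate among the 40 kept is

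p_e = (0.60 × 44 − 4q) / 40 = (26.4 − 4q) / 40.

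| q | p_e | P(X ≥ 30), one-sided rule | P(X ≥ 31), two-sided rule |
|---|---|---|---|
| 0% | 66.0% | 15.0% | 8.3% |
| 30% | 63.0% | 7.7% | 3.8% |
| 50% | 61.0% | 4.6% | 2.1% |
| 60% | 60.0% | 3.5% | 1.6% |
| 80% | 58.0% | 2.0% | 0.8% |

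The one-sided error passes 5% when *q* is below about 47%. The two-sided rule passes its 2.5% upper tail when *q* is below about 45%. With a single man excluded (43 kept, rule 32/43), the worst case is 5.2%.

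**3. What an all-treated analysis would show.** With 44 men the one-sided rule is 33/44 (attained error 2.8%). If the four men without a PSA count as non-responders:
- 30/40 (p = 0.035) becomes 30/44 = 68.2% (p = 0.170).
- 32/40 (p = 0.006) becomes 32/44 = 72.7% (p = 0.056).

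Its power is 84.6% if the all-treated rate is 80%. If 80% holds only among men with a PSA, the all-treated rate is 0.80 × 40/44 = 72.7% and power is 44.3%. With exactly 10% missing, the rate is 0.90 × 0.80 = 72% and power is 40.1%.

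**4. Status of a man with metastasis during treatment.** Section 14.5 recognises distant clinical failure, so the second route would count him as a non-responder. The 9.1 list does not include metastasis, so read alone it would not. Section 4.11 keeps him in an analysis that Section 14 does not define, and Section 12 is silent. At the boundary one such man matters: 30/40 gives p = 0.035 and 30/41 gives p = 0.057.

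**The case against.** The strongest reply is that the second route keeps the likeliest non-responders (early failures and prostate-cancer deaths) and scores them as such. That is correct, and it limits the bias. Other exclusions, such as a missed visit or an unrelated death, need not be linked to PSA response. The 10% drop-out allowance may also include men who were never treated, whose removal does not cause this bias. The trial is meant to inform a later one, and the primary result is reported as an estimate with an interval. All of this stands; it makes the inflation conditional, but does not supply the missing analysis.

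Four stronger readings are tempting, and the documents do not support them:
- *The plan breaks a general intent-to-treat promise.* Section 4.11 has one clause, limited to men removed for metastasis, and the second route may satisfy it. Section 12 omits the clause but does not remove these men from analysis. What remains is an undefined term.
- *Men with metastasis are excluded.* Section 14.5 counts distant failure as clinical failure and Section 9.2.4 scores hematogenous relapse. The fault is an incomplete 9.1 definition.
- *Men who start other therapy drop out.* A man who completes radiotherapy and has the nine-month PSA stays in, possibly as a responder. The gap is that 14.3 has no scoring rule for him, although Table 14.5 counts subsequent therapy as an event for failure rate and failure-free survival.
- *The null is rejected too easily as a matter of course.* At *q* = 50% the one-sided error is 4.6%, still below nominal. Taking 10% literally with no responders among the excluded gives 0.60/0.90 = 66.7% and 17.1%, but the planned 4 of 44 gives 15.0%, and only at that extreme.

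**Conclusion.** The point holds in a limited form. The main set is defined by post-treatment events, some treated non-responders can leave the denominator, and no all-treated analysis would show how much that matters. With 4 of 44 treated men excluded and a true all-treated rate of 60%, the chance of a positive result lies between 3.5% (no bias) and 15.0% under the one-sided rule, and between 1.6% and 8.3% under the two-sided rule, for *q* from 60% down to 0%. If excluded men respond more often than 60%, the bias runs the other way. These figures rest on the assumed *q* and on the assumed number of treated men excluded. The handling of metastasis is an ambiguity across Sections 4.11, 9.1, 12 and 14.5, and does not show that these men are left out. The point should be fixed before the primary analysis, but it does not invalidate the design.

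**What to change.** 1. In Section 14.3, prespecify a sensitivity analysis of the primary endpoint in all eligible men who receive a first fraction, with no valid PSA at the endpoint time counted as non-response. Report it beside the evaluable-set result. It needs one endpoint time: evaluability is now tied to nine months and the endpoint to 21 months, so a man with the nine-month but no 21-month PSA is evaluable without a scoring rule. Reconcile the two first.
2. State in 14.3 that metastasis found during or after radiotherapy, before the endpoint PSA, counts as clinical failure and so as non-response. Align the 9.1 definition with 14.5. Give Sections 4.11 and 12 the same sentence on analysis sets, naming a set that Section 14 defines.
3. State how anticancer therapy started before the endpoint PSA is scored, exempting androgen deprivation planned with the radiotherapy, which Section 3.2 allows.

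The cost is some wording and one extra table. The all-treated rate will look slightly less favourable. Its power is only about 40% to 44% if about 10% are missing and 80% of the rest respond, which is why it should remain a sensitivity analysis and not replace the main one.
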